8.5 Product Removal

In the unlikely event that a participant is intolerant of the study product immediately after placement, the site clinician will remove any residual drug with a sterile saline wash and a moistened swab if necessary.

8.6 Criteria for Early Termination of Study Participation

Participants may voluntarily withdraw from the study for any reason at any time. The Site Pl/designee also may withdraw participants from the study to protect their safety and/or if they are unwilling or unable to comply with required study procedures. Participants also may be withdrawn if the study sponsors, government or regulatory authorities, including the Office of Human Research Protections (OHRP), or site IRBs/ECs terminate the study prior to its planned end date. Every reasonable effort is made to complete a final evaluation of participants who withdraw or are withdrawn from the study prior to completing follow-up. Study staff members will record the reason(s) for all withdrawals in participants' study records.

9 STATISTICAL CONSIDERATIONS

9.1 Review of Study Design

This is a first in human multi-day dose phase 1 randomized, double-blind, placebo-controlled study to evaluate safety after 14 doses of Q-GRFT prepared in saline. The primary aim of the study is to assess the local and systemic safety of nasally administered Q-GRFT in healthy adults. The primary endpoint is the proportion of participants who experience a Grade 2 or higher related adverse event.

9.2 Sample Size and Accrual

Accrual of approximately 45 evaluable participants is expected to take 6 months. The expected duration of study participation for each participant will be approximately 6-8 weeks. This includes the screening period. Participants will be randomized 2:1 (Q-GRFT nasal spray: placebo nasal spray) resulting in 30 participants enrolled into the Q-GRFT arm and 15 participants enrolled into the placebo arm.

The primary aim of the study is to assess the local and systemic safety of nasally administered Q-GRFT in healthy adults. The primary endpoint is the proportion of participants who experience a Grade 2 or higher adverse event deemed related to study product. The proposed total sample size is N=45 divided into 2 arms (Q-GRFT and placebo assigned at a 2:1 ratio). The sample size is based on the exact binomial probability of observing at least two Grade 2 or higher related adverse events in the Q-GRFT arm. Table 1 gives the upper and lower bounds for the 95% exact binomial confidence intervals of the true Grade 2 or higher adverse event rate at all possible numbers of observed events in a group of size 30. Note that the results for more than 50% of events in each group are not listed, but by symmetry can be calculated as 1- the listed rate and 95% CI for the number of non-events. If none of the 30 participants experience Grade 2 or higher adverse event rate is 11.6%. In a Cochrane review of intranasal steroids for rhinosinusitis, the rate of any adverse event was 5.5%⁸. If similar event rates are observed in the proposed study, we will be able to rule out Grade 2 or higher adverse event rates greater than 22.1% in the Q-GRFT study arm.

Number of	
observed	Rate (95% CI)
events	
0/30	0 (0, 11.6%)
1/30	3.3% (0.1%, 17.2%)
2/30	6.7% (0.8%, 22.1%)
3/30	10.0% (2.1%, 26.5%)
4/30	13.3% (3.8%, 30.7%)
5/30	16.7% (5.6%, 34.7%)
6/30	20.0% (7.7%, 38.6%)
7/30	23.3% (9.9%, 42.3%)
8/30	26.7% (12.3%, 45.9%)
9/30	30.0% (14.7%, 49.4%)
10/30	33.3% (17.3%, 52.8%)
11/30	36.7% (19.9%, 56.1%)
12/30	40.0% (22.7%, 59.4%)
13/30	43.3% (25.5%, 62.6%)
14/30	46.7% (28.3%, 65.7%)
15/30	50.0% (31.3%, 68.7%)

 Table 9: 95% confidence intervals for the true rate at all possible observed Grade 2 or higher

 adverse event rates

9.3 Study Endpoints

9.3.1 Primary Endpoint

The proportion of participants who experience a related Grade 2 or higher adverse event.

9.3.2 Secondary Endpoints

Persistence: Q-GRFT concentrations from nasopharyngeal swabs 1) collected 24 hours after a single dose and 2) collected 24 hours after 13 consecutive daily doses

Pharmacokinetics: Q-GRFT concentrations in plasma 1) 24 hours after the first dose and 2) 24 hours after the 13th consecutive daily dose

Acceptability: Self-reported assessment of qualities of the experience with the nasal spray as assessed by acceptability questionnaires. Product attributes considered likely to discourage future use by participants, will be dichotomized as having a rating of lower than 3 on a 5-point Likert scale.

9.3.3 Exploratory Endpoints

Change in Brief Smell Identification Test (BSIT) score after 13 days of consecutive daily doses compared to baseline

Persistence: Q-GRFT concentrations from oropharyngeal and nares swabs collected 1) 24 hours after first dose and 2) 24 hours after the 13th consecutive daily dose

Presence: Q-GRFT concentrations from rectal swab collected 24 hours after the 13th consecutive daily dose

Immunogenicity of Q-GRFT study product delivered by an intranasal spray system

Humoral antibody responses to Q-GRFT in plasma/blood by ELISA

9.4 Blinding and Unblinding

Blinding will be maintained until all data are entered into the study database, all study endpoint data and other data included in the final analysis have been cleaned and verified, and the data are ready for final analysis.

Unblinding may need to be performed on an individual basis for assessment of a serious AE and/or for the safety of the participant. Details of emergency unblinding are specified in an SOP.

9.5 Randomization

The randomization scheme will be generated and maintained by a member of the Data Management Center at Magee-Womens Research Institute and supplied to the Pharmacy at Magee-Womens Hospital. Participants will be randomized to the sequence of the two nasal spray formulations, active or placebo, in a 2:1 ratio using a permuted block design with random block sizes of 3 and 6. To minimize bias in the group assignment, participants will be given study randomization numbers. Participants will be randomized using REDCap's randomization module to obtain the sequence of product assignment. When a participant is ready to be randomized, the study investigator (PI/Co-I) will open the Randomization eCRF in REDCap and confirm that the participant is being enrolled. REDCap will then assign a randomization number which the study investigator (PI/Co-I) will print and take to the pharmacy to obtain the study product indicated by the randomization scheme. The study product will be labeled in order to mask the product assignment to the participants and study staff. The randomization scheme will be created for a total of 48 participants.

9.6 Data Monitoring and Analysis

9.6.1 Data Monitoring

PREVENT V.5.0

This clinical trial will be conducted in compliance with the protocol, GCP guidelines, and applicable regulatory requirements. All paper research charts are maintained in locked files in a locked room. The data management research staff, under the direction of the primary investigator, will create and maintain databases using REDCap (Research Electronic Data Capture) which is a secure, validated, web-based application designed for clinical trial data collection. The databases will be backed up nightly, weekly, and monthly onto the University of Pittsburgh's server's back-up system. Appropriate firewall and virus scanning software are installed and updated routinely by the university support staff.

This study will utilize electronic data capture. Site staff will enter data as collected directly into a data entry system. Study data management staff will review the electronic data elements for completeness and accuracy. If there are any responses that are incomplete, unclear, or inconsistent with related data elements, the staff person will communicate with the clinician in question as soon as possible to resolve the problem. If necessary, the study staff will make the appropriate change in the electronic database which tracks time, date, and by whom a change is made.

9.6.2 Statistical Analysis

The number of adverse events will be summarized by severity, body system, and relationship to study product using frequencies and percent. Individual participants will contribute once to the calculation of event rates. Differences in the prevalence of adverse events between the study arms will be assessed using Fisher's exact test.

Descriptive statistics (frequency, medians, range, means, standard deviation) will be used to summarize the secondary and exploratory endpoints. Differences in Q-GRFT concentration and BSIT score between the study arms will be evaluated using Student's t- or Mann Whitney U tests, where appropriate. Fisher's exact tests will be used to assess differences in the presence of Q-GRFT in the gastrointestinal tract and dichotomized acceptability endpoints between the two study arms. Spearman's correlation coefficients Fisher's exact, and Mann-Whitney U tests may be used in exploratory analyses to evaluate the impact of gender, age and race on the pharmacokinetics and acceptability of the Q-GRFT nasal spray.

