2.5 PK Data: Q-GRFT

Intranasal administration of Q-GRFT to rats and rabbits indicated low levels of Q-GRFT reach systemic circulation with this route of administration. In a rat PK/BA study of Q-GRFT, very low levels of systemic exposure were observed after QD and BID intranasal administration, with highest plasma level of 14.44 ng/mL, which corresponds to an estimated 0.15% of dose administered In a 30 day multi-dose study, rats with once daily or twice daily intranasal administration, low levels of Q-GRFT in plasma (1.02 – 21.6 ng/mL) were detected in some animals up to 14 hours post-dose. Single day intranasal administration of Q-GRFT nasal solution (same as clinical formulation) to rabbits showed mean apparent Cmax of 17.1 ng/ml (male) at a

dose of 1.5 mg and 137 ng/ml (males) and 63.2 ng/ml (females) at the 3 mg dose. Q-GRFT was eliminated with a mean terminal t1/2 of 15.8 hr (males) and 18.8 hr (females) in the 3 mg intranasal group. Repeated daily intranasal administration of Q-GRFT nasal solution to rabbits for 15 days showed that the mean apparent Cmax on Day 15 was 61.7 ng/ml (female) at a dose of 1.5 mg, and 63.3 ng/ml (males) and 147 ng/ml (females) at a dose of 3 mg. Plasma exposure to Q-GRFT was 2.5-fold greater with the BID regimen versus the QD regimen in the intranasal groups on Day 15, based on AUC_{last} values. The mean AUC_{last} was 1,866 hr*ng/ml in 3 mg dosed females and 733 hr*ng/ml in 1.5 mg dosed females on Day 15. The bioavailability of intranasal Q-GRFT is 0.1% in Phase B after repeated administrations, and therefore, accumulation is unlikely to be an issue in human studies. A slight (~2x single exposure), increase in exposure was seen with repeat dose intranasal (3 mg dose), however, this increase was statistically non-significant (P>0.05) and observed in only few animals.

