Results of a single-administration PK/BA study showed that the average t1/2 of Q-GRFT DS delivered intravenously (IV) in male and female Sprague-Dawley rats is 6-7 hours (Study B949-17; see IND 130697). Single dose of IV administered Q-GRFT in male and female rabbits also showed a similar terminal t1/2 of 7.7-9.4 h. Whereas, 15-day daily IV administration of Q-GRFT had a mean terminal t1/2 of 29.0 h in males and 26.0 h in females after IV administration on Day 15 and was longer than that observed on Day 1 of single dose study. Although not evaluated in same animals, repeat dose administration of Q-GRFT for 15 days seems to have resulted in Q-GRFT accumulation in plasma. The mean AUC_{last} on Day 15 (74,825 h*ng/ml in males and 96,992 h*ng/ml in females) was over 5-fold greater than the mean AUC_{last} on Day 1 (13,454 h*ng/ml in males and 17,329 h*ng/ml in females) in IV Group 5 (1.29 mg Q-GRFT). The accumulation of Q-GRFT on Day 15 in the IV group might be due to a saturation of metabolism and/or elimination pathways of the API. Q-GRFT was not bioavailable intrarectally at either the 0.3% (2.5 mg/kg) or 3.0% (25 mg/kg) Q-GRFT formulations. The amount of Q-GRFT to be applied intranasally is significantly less than the rectal dose and Q-GRFT is not expected to be systemically absorbed in significant levels from the nasal application.

Similarly, analyses of rat and rabbit sera from animals administered Q-GRFT carbopol formulations in GLP-compliant studies (21-day repeat-dose plus 14-day recovery, Studies M333-17 and M334-17) showed no Q-GRFT in any of the samples. These results demonstrated that neither Q-GRFT DS nor gel-formulated DP are absorbed systemically when delivered intrarectally to rats and rabbits for up to 21-consecutive days at doses up to 3% API.

In PREVENT HIV, the Phase 1 study examining safety and tolerability of rectal administration of Q-GRFT, Q-GRFT was not detectable in plasma after administration in any participant.

The length of time that Q-GRFT persists in the nasal mucosa after intranasal administration in humans is currently not known and will be examined in this trial. Based on in vivo studies in rats and rabbits, intranasal administration of Q-GRFT may result in low levels of systemic exposure.

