3 OBJECTIVES

3.1 Primary Objective:

PREVENT V.5.0

• To assess the local and systemic safety of intranasal Q-GRFT after 14 doses

3.2 **Primary Endpoint:**

• The proportion of participants who experience a related Grade 2 or higher adverse event

3.3 Secondary Objectives:

- Persistence: To determine the persistence of Q-GRFT in the respiratory tract after a single dose and after 13 days of daily use as assessed by nasopharyngeal swab
- Pharmacokinetics: To determine the systemic absorption of Q-GRFT after administration of a single dose and after 13 days of daily use
- Acceptability: To assess the acceptability of a Q-GRFT nasal spray

3.4 Secondary Endpoints:

- Persistence: Q-GRFT concentrations from nasopharyngeal swabs collected 24 hours after a single dose and 24 hours after 13 consecutive daily doses
- Pharmacokinetics: Q-GRFT concentrations in plasma 24 hours after the first dose and 24 hours after the 13th consecutive daily dose
- Acceptability: Self-reported assessment of qualities of the experience with the nasal spray through a Likert scoring of acceptability questions

3.5 Exploratory Objectives:

- To assess the impact of Q-GRFT nasal spray on smell
- Persistence: Q-GRFT concentrations from oropharyngeal and nares swabs collected 24 hours after a single dose and 24 hours after 13 consecutive daily doses
- Presence of Q-GRFT in the gastrointestinal tract after 13 days of consecutive use
- Determine the potential of the Q-GRFT study drug product to induce an immune response by measuring the generation of anti-drug antibodies (ADAs) in plasma/blood samples after multiple Q-GRFT intranasal spray treatments

3.6 Exploratory Endpoints:

- Change in Brief Smell Identification Test (BSIT) score after 13 days of consecutive daily doses compared to baseline
- Persistence: Q-GRFT concentrations from oropharyngeal and nares swabs collected 24 hours after first dose and 24 hours after the 13th consecutive daily dose
- Presence: Q-GRFT concentrations from rectal swab collected 24 hours after the 13th consecutive daily dose
- Immunogenicity of Q-GRFT study product delivered by an intranasal spray system
- Humoral antibody responses to Q-GRFT in plasma/blood by ELISA

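### Section 9.6.2 leaves the BSIT comparison undefined and unadjusted for baseline, and reports Q-GRFT concentration without intervals and with a test only against vehicle (secondary and exploratory endpoints)

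*Combined protocol and SAP*

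**What the plan says.** Section 9.6.2 gives the whole analysis of these endpoints. It opens with "Descriptive statistics (frequency, medians, range, means, standard deviation) will be used to summarize the secondary and exploratory endpoints". It then says "Differences in Q-GRFT concentration and BSIT score between the study arms will be evaluated using" Student's t or Mann-Whitney U tests, as appropriate. Fisher's exact test is named for the presence of drug in the gastrointestinal tract and for dichotomised acceptability. Optional analyses by gender, age and race may follow. No confidence interval, baseline adjustment or within-participant comparison is named for these endpoints.

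The endpoints themselves are more specific. Section 9.3.3 defines the BSIT endpoint as a change from baseline after the 13-day course. Section 7.3 takes a BSIT before the first dose at Visit 2 and another about one hour after it. Section 7.5 (Table 4) takes one again at Visit 4, when the 13-day course starts.

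For concentration, Section 3 asks for "the persistence of Q-GRFT in the respiratory tract after a single dose and after 13 days of daily use", and Section 9.3.2 lists "Q-GRFT concentrations in plasma 1) 24 hours after the first dose and 2) 24 hours after the 13th consecutive daily dose". The comparator is a matched vehicle (Section 6.3). Section 2.5 says "Q-GRFT is not expected to be systemically absorbed in significant levels from the nasal application".

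Elsewhere the plan does use intervals: Section 9.2 tabulates "the upper and lower bounds for the 95% exact binomial confidence intervals" for adverse events in a group of 30.

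**The concern.** **BSIT.** One sentence covers the test, and two analysts could follow it and report different things: a difference in Visit 6 scores, a difference in change from Visit 2, or a difference in change from Visit 4. By Visit 4 the participant has already had one dose, so the two candidate baselines do not mean the same thing. Under any of these readings a collected pre-dose score is used less efficiently than it could be.

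**Concentration.** A test against vehicle asks whether drug is detectable above assay background. That is a fair question for plasma and rectal samples, but where few values are quantifiable the test has little power. A p-value above 0.05 could then be taken to mean that nothing is absorbed. Means and SDs without intervals would not correct that impression, and 9.6.2 gives no rule for values below quantification.

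**Working it through.** **Plan's own figure.** Table 9, 0 of 30: upper exact limit = 1 − 0.025^(1/30) = 11.6%, as printed. All 16 rows reproduce by the Clopper-Pearson formula. The arm sizes of 30 and 15 follow from 45 split 2:1.

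**Test against vehicle.** Assume all 15 vehicle values are unquantifiable and k of 30 active values are quantifiable, with unquantifiable values tied lowest. Two-sided p-values:

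| k/30 | Fisher | Mann-Whitney, permutation | Mann-Whitney, normal approximation |
|---|---|---|---|
| 6 | 0.157 | 0.13 | 0.070 |
| 7 | 0.077 | 0.077 | 0.047 |
| 8 | 0.038 | 0.039 | 0.032 |

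An exact test therefore needs k ≥ 8. At k = 7 the conclusion depends on how the p-value is computed, which 9.6.2 does not state. With K ~ Binomial(30, π), P(K ≥ 8) = 0.008, 0.239 and 0.719 for π = 0.10, 0.20 and 0.30. The exact 95% interval shows the uncertainty directly: 0/30 gives 0 to 11.6%, and 3/30 gives 2.1 to 26.5%.

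**BSIT.** The documents give no SD or correlation, so work in SD units with an assumed baseline correlation ρ. The half-width of the 95% CI is t × √(1/30 + 1/15) × f, with t about 2.02 and √0.1 = 0.316. The factor f is 1 for final score, √(2(1−ρ)) for change and √(1−ρ²) for ANCOVA.

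| ρ | Final score | Change | ANCOVA | ANCOVA variance cut vs final | vs change |
|---|---|---|---|---|---|
| 0.3 | 0.64 | 0.75 | 0.61 | 9% | 35% |
| 0.5 | 0.64 | 0.64 | 0.55 | 25% | 25% |
| 0.7 | 0.64 | 0.49 | 0.46 | 49% | 15% |

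The cuts are 1 − (1−ρ²) against final score and 1 − (1−ρ²)/(2(1−ρ)) against change. Change alone beats the final score only when ρ > 0.5.

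**Optional paired ratio, Visit 6/Visit 3.** The 95% CI factor is exp(t × SDw × √(2/m)) for m pairs, with SDw the assumed within-subject SD on the log scale (no human value is given).

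| m | SDw 0.5 | 0.8 | 1.0 | 1.2 |
|---|---|---|---|---|
| 30 | 1.30 | 1.53 | 1.70 | 1.88 |
| 15 | 1.48 | 1.87 | 2.19 | 2.56 |
| 9 | 1.72 | 2.39 | 2.97 | 3.69 |

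Keeping only pairs with both values quantifiable biases the ratio toward 1. In simulation with a true ratio of 2 and 80% of pairs qualifying, it reads about 1.8 with equal within- and between-subject log-SDs (0.5 to 1.0), and 1.67 to 1.71 with a between-subject SD of 0.4 and a within-subject SD of 0.8 to 1.2. The shortfall is roughly 10 to 16%. At a true ratio of 3 (within 0.8, between 0.4) it reads 2.44, about 19% low.

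**Timing.** Section 7.9 allows Visit 3 at 24 to 48 hours. Section 2.5 reports "a mean terminal t1/2 of 15.8 hr (males) and 18.8 hr (females) in the 3 mg intranasal group" for rabbit plasma. If those half-lives applied, a 48-hour sample would read low by 2^(24/18.8) = 2.4 to 2^(24/15.8) = 2.9 times. Accumulation at 24 hours, 1/(1 − 2^(−24/h)), would be only 1.5 to 1.7, so the timing error could exceed the effect sought. Twelve doses rather than 13 changes the level by under 0.01%.

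**The case against.** The endpoint is explicitly change from baseline, so the BSIT score in 9.6.2 may simply be shorthand for it. This stands. A reader might infer that the BSIT test ignores the baseline, but the documents do not establish that; they leave the tested quantity and the baseline visit open.

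A reader might also infer that a pharmacokinetic objective goes unanswered without a Visit 6/Visit 3 comparison. The documents do not support that. The objectives ask for levels at two separate times, and the planned summaries provide them. Section 2.5 does discuss accumulation, but of the rise in rabbits it says "this increase was statistically non-significant (P>0.05) and observed in only few animals", so it is context only.

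Nor does any text say that a non-significant vehicle comparison will be read as no absorption. Frequencies are already planned, pre-dose Visit 2 samples of blood and the three respiratory sites give a further background check, and assay methods sit in SOPs outside these documents. The vehicle test is therefore a legitimate background check. Its low power where few values are quantifiable remains, as does the absence of intervals.

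Finally, BSIT is a 0 to 12 count in healthy adults and may cluster near the top, where a linear model fits less well. That is a fair limit on ANCOVA and is met by keeping a rank-based check.

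**Conclusion.** The point holds as an underspecified and inefficient analysis of secondary and exploratory endpoints. It is not a contradiction, and it does not touch the primary endpoint or the sample size.

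- BSIT: what is tested and which visit is baseline are not stated, and no adjustment is planned. The gain from ANCOVA is 9 to 49% of variance against final score and 15 to 35% against change, over assumed correlations of 0.3 to 0.7. At 0.3 the gain over the final score is small.
- Concentration: with no quantifiable vehicle values, an exact test rejects about 1%, 24% and 72% of the time at true rates of 10%, 20% and 30%. Non-rejection is weak evidence of no absorption.
- The paired ratio is informative only where most pairs are quantifiable, and its size rests on assumed SDs and, for timing, on a rabbit plasma half-life. Section 2.5 says that human nasal persistence is not yet known.

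**What to change.** Amend Section 9.6.2 before unblinding, for secondary and exploratory endpoints only.

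1. BSIT: compare Visit 6 scores between arms by ANCOVA on the pre-dose Visit 2 score, with a 95% CI. Name that score as the baseline and keep a rank-based check.
2. Concentration: within the Q-GRFT arm, report number and percent quantifiable with exact 95% CIs at Visits 3 and 6 for each sample type (Visit 6 only for the optional rectal swab, with the number of swabs taken). Rank unquantifiable values as tied lowest. Use an exact or permutation p-value for the vehicle comparison, and state that non-rejection is not evidence of no absorption.
3. Optional and supportive: a paired Visit 6/Visit 3 geometric mean ratio with 95% CI where most pairs are quantifiable, giving the number of pairs and noting the bias toward 1. Add a sensitivity analysis on recorded hours since last dose, with a prespecified window compatible with the 24 to 48 hour Visit 3 window. A restriction to participants who took all 13 doses is not needed.

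Items 1 and 2 use data already collected and cost a little analysis work. Item 3 also needs the clock time of the Visit 2 dose: the administration log covers the 13-day course, and the documents do not say that the first dose time is recorded. No new sample or visit is required.

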7.3 Visit 2: Enrollment

Subjects who meet the inclusion and exclusion criteria following the Screening visit may schedule an Enrollment visit. This visit is to occur within 60 days of the Screening Visit.

At this visit, locator information will be updated, and eligibility reviewed. Participants will undergo a smell assessment prior to drug delivery. The Brief Smell Identification Test (BSIT) contains 12 odorants embedded on scent strips and released when scratched with a pencil tip. The BIST is a forced choice test as participants are instructed to identify an odorant even if no smell is perceived. The total olfaction score using the BSIT is defined as the number of odorants that are correctly identified.

The participant will be sequence randomized to receive either Q-GRFT nasal spray or placebo nasal spray. The clinician will administer the first dose of study product. After reviewing administration instructions, the participant will try the metered dose delivery system by delivering product into a paper towel. Participants will be asked to wait at the research trial site for one hour after product administration for observation. All participants will undergo an assessment of adverse events, targeted physical exam, blood draw, and assessment of smell approximately one-hour postnasal spray administration.

Interested participants may participate in an optional enrollment visit sampling (nasal, oropharyngeal, and nasopharyngeal) at a single timepoint between 1- and 12-hours post product administration. Participants must agree to all three sample collections to be eligible for this optional enrollment visit sampling.

VISIT 2: ENROLLMENT – PRE		
Component	Procedure/Analysis	
ADMINISTRATIVE	 Review/Confirm Eligibility Collect/Update Contact Information Visit Questionnaire Quality of Life Survey Update Medical History and Concomitant Medications Provide Available Screening Results Protocol Counseling 	
URINE	Pregnancy Test (participants of childbearing potential)	
PHYSICAL EXAM	 Targeted Physical Exam Assessment of Smell (BSIT) Vital Signs (BP) 	
BLOOD	 Q-GRFT level ADA test for Anti Q-GRFT antibodies	
NASAL	Q-GRFT level	
OROPHARYNGEAL	Q-GRFT level	
NASOPHARYNGEAL	Q-GRFT level	
STUDY PRODUCT	 Randomized to study product Study Product Provision Clinician-administered 	
1-HR POST-DOSE		
Component	Procedure/Analysis	
ADMINISTRATIVE	 Assess/Document Adverse Events Schedule Next Study Visit Participant Reimbursement 	

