9.6.3 Analysis Cohort

The intent-to-treat cohort (ITT) will be defined as those who were enrolled. It will be used for analyses of baseline characteristics, protocol deviations and violations, and trial conduct. The evaluable cohort (Eval) is a subset of ITT participants. Evaluable participants will be defined as participants who complete Visit 6 procedures.

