10.2 Informed Consent Process

Written informed consent will be obtained from all potential study participants prior to the initiation of any study-related procedures. The informed consent process will give individuals all the relevant information they need in order to decide whether to participate, or to continue participation, in this study. Potential research participants will be permitted to ask questions and to exchange information freely with the study investigators. Only listed study investigators may obtain informed consent from potential study participants. The investigators will keep research participants fully informed of any new information that could affect their willingness to continue study participation.

Risk/Benefit Statement

Risks

It is not expected that this study will expose healthy participants to unreasonable risk. While this is the first in human multi-day dose assessment of Q-GRFT administered intranasally, Q-GRFT is under evaluation n a Phase I clinical trial as a rectal enema product for HIV prevention at Magee-Womens Research Institute within an NIAID U19 funded collaboration between the University of Pittsburgh and the University of Louisville (U19 AI113182, [name] Program Director). No safety issues have been identified to date in 15 healthy volunteers who have received a single dose enema containing 10mg/mL of Q-GRFT in phosphate buffered saline.

As with any intranasally administered product, nasal congestion, nasal discharge, nasal burning, nasal irritation, increased mucus, nasal dryness, sneezing, coughing, pharyngitis, epistaxis, mucosal erythema, nasal ulceration, interference with taste and smell, tinnitus, and headache are potential risks and participants will be closely monitored for these. Hypersensitivity reactions (including contact dermatitis and rash) are rare risks with any product. As the drug is intended to work at the mucosal surface, systemic side effects are presumed to be exceptionally unlikely. Nonetheless, safety labs including CBC with platelets, AST, ALT, total bilirubin and creatinine will be checked pre and post administration.

A rare but potentially life-threatening risk of exposure to nasal spray containing Q GRFT or the placebo spray would be anaphylaxis. Risk will be mitigated by having the single application of the product in the clinical research site and having people remain in the clinical trial facility for 1 hour after application.

Additional Risks:

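### Section 9.6.2 compares BSIT between arms without adjusting for the pre-dose score already collected; for most plausible correlations, adjustment would be more precise at the cost of one degree of freedom

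*Combined protocol and SAP*

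**What the plan says.** - **Endpoint.** Section 9.3.3 (also the Protocol Summary and Section 3.6) defines the exploratory smell endpoint as "Change in Brief Smell Identification Test (BSIT) score after 13 days of consecutive daily doses compared to baseline".
- **Score.** Section 7.3 says of the test, which has 12 odorants: "The total olfaction score using the BSIT is defined as the number of odorants that are correctly identified". The score is therefore a whole number from 0 to 12.
- **Analysis.** Section 9.6.2 says that descriptive statistics "will be used to summarize the secondary and exploratory endpoints". It continues: "Differences in Q-GRFT concentration and BSIT score between the study arms will be evaluated using" Student's t or Mann-Whitney U tests, as appropriate. No covariate is named.
- **Timing.** At Visit 2, "Participants will undergo a smell assessment prior to drug delivery", and there is a second "assessment of smell approximately one-hour postnasal spray administration". BSIT is repeated at Visits 3, 4, 5, 6 and 7 (Tables 3 to 7, Appendix 1). The word baseline is not tied to a visit.
- **Cohort.** Section 9.6.3: "Evaluable participants will be defined as participants who complete Visit 6 procedures". Table 6 lists BSIT among the Visit 6 procedures.

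**The concern.** The variable named in the test and the variable named in the endpoint are worded differently, so there are two readings. Taken literally, the test uses the raw Visit 6 count and ignores the pre-dose score. Taken as shorthand for the endpoint, it uses the change, and the pre-dose score enters only by subtraction. A regression adjustment would use that score better than either, over most of the range of r.

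What is at stake is precision. BSIT is the only smell test in the visit tables, and the comparison rests on about 30 vs 15 participants. The pre-dose score is taken at Visit 2 and evaluable participants complete Visit 6, so both values should exist for each of them. No new data are needed.

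**Working it through.** **Inputs from the plan:** 45 evaluable participants, 2:1, hence 30 vs 15 (Section 9.2); BSIT before the first dose (Section 7.3) and at Visit 6 (Section 7.7). The plan gives no SD, correlation, effect size or power for BSIT, so it has no figure of its own to reproduce here. Table 9 concerns adverse events only.

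**Assumptions:** the same SD at both visits and in both arms; r is the correlation between the observed pre-dose and Visit 6 scores, varied over a range.

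**Formulas** (SE of the arm difference, in SD units):

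- s = √(1/30 + 1/15) = 0.316
- Raw Visit 6 score: s
- Change: s × √[2(1 − r)]
- ANCOVA: s × √[(1 − r²) × 42/41], where 42/41 = (N − 3)/(N − 4) is the cost of estimating the slope with N = 45

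| r (assumed) | SE raw | SE change | SE ANCOVA | ANCOVA vs change | ANCOVA vs raw |
|---|---|---|---|---|---|
| 0 | 0.316 | 0.447 | 0.320 | 28% lower | 1% higher |
| 0.1 | 0.316 | 0.424 | 0.319 | 25% lower | 1% higher |
| 0.3 | 0.316 | 0.374 | 0.305 | 18% lower | 3% lower |
| 0.5 | 0.316 | 0.316 | 0.277 | 12% lower | 12% lower |
| 0.7 | 0.316 | 0.245 | 0.229 | 7% lower | 28% lower |
| 0.8 | 0.316 | 0.200 | 0.192 | 4% lower | 39% lower |
| 0.96 | 0.316 | 0.0894 | 0.0896 | 0.2% higher | 72% lower |

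**Where the gain stops:**

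- Against raw: (1 − r²) × 42/41 < 1 requires r² > 1/42, so r > 0.154.
- Against change: (1 − r²) × 42/41 < 2(1 − r) requires 1 + r < 82/41 × 41/42 = 1.952, so r < 0.952.
- Largest loss: 42/41 − 1 = 2.4% of variance, reached against raw at r = 0 and approached against change as r nears 1.

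**Illustration with a ceiling.** Simulated whole-number scores capped at 12 (10,000 trials per setting, latent mean 11.5, latent SD 1.2, active arm lowered by one latent point, two-sided 5%). Effect and distribution are invented. Rounding and capping pull the observed r below the latent r, so both are shown.

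| Latent r | Observed r | t on raw | t on change | ANCOVA | Rank ANCOVA |
|---|---|---|---|---|---|
| 0.1 | 0.08 | 64.9% | 44.8% | 63.7% | 65.0% |
| 0.5 | 0.42 | 65.6% | 64.8% | 73.7% | 73.8% |
| 0.9 | 0.82 | 64.9% | 98.4% | 98.0% | 97.0% |

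With no effect, ANCOVA rejected in 4.6% to 5.4% of trials across the settings run. At observed r = 0.82 ANCOVA's variance equalled that of change (ratio 1.000), whereas the equal-SD formula would give 1.82/2 × 42/41 = 0.93. A ceiling can therefore remove the gain over change at high r.

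**The case against.** The strongest case against acting has four parts.

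1. **The plan's test is valid.** A t or Mann-Whitney test on change, or on the raw score, is unbiased under randomization. This stands: the point is about efficiency, not error.
2. **The natural reading is change.** The endpoint is defined that way and the preceding sentence of 9.6.2 refers to the endpoints. On that reading, with r of 0.7 to 0.8, the SE gain is only 7% to 4%. The larger gains (28% and 39%) need the raw-score reading. This also stands, although r is unknown and at 0.3 to 0.5 the gain over change is 18% to 12%.
3. **The endpoint is exploratory.** It has no hypothesis or power, and the sample size rests on related Grade 2 or higher adverse events. Noticeable smell loss has another route, since "interference with taste and smell" is among the risks for which Section 10.2 promises close monitoring. This sets the priority low.
4. **Linear ANCOVA does not replace the Mann-Whitney option for a skewed, capped score.** Correct, so the fix needs a rank-based form. In the simulations its power was within about 1.5 points of linear ANCOVA.

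A reader might go further and infer that adjustment is always more precise and costs nothing. The arithmetic does not support that. It loses slightly to the raw score at r below about 0.15 and to change at r above about 0.95. A low r cannot be excluded, because healthy adults may cluster near 12.

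**Conclusion.** The point holds as a low-priority improvement. Adjusting Visit 6 BSIT for the Visit 2 pre-dose score is more precise than both readings of 9.6.2 for r between about 0.15 and 0.95, and loses at most about 2.4% of variance outside that range. This rests on 30 vs 15, equal SDs and an r that the documents do not supply. The power figures are illustrative only.

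The balance favours adjusting. Choosing the raw score is costly if r is high, and choosing change is costly if r is low. ANCOVA stays close to the better of the two throughout.

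A reader might also infer that the planned smell comparison is biased, or that it discards the baseline. The documents do not support either: randomization protects both readings, and the endpoint definition allows the change reading. The primary safety conclusion is unaffected.

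**What to change.** In Section 9.6.2, replace the BSIT part of the sentence with text to this effect:

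> Visit 6 BSIT will be compared between arms by ANCOVA with the Visit 2 pre-dose BSIT as covariate, reporting the adjusted difference and 95% CI. Where scores are skewed or at the ceiling of 12, a rank-based ANCOVA (ranks of Visit 6 BSIT on arm and ranks of Visit 2 pre-dose BSIT) will be used in place of the Mann-Whitney test. Change from Visit 2 pre-dose to Visit 6 will be summarized by arm.

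The words pre-dose matter because BSIT is done twice at Visit 2 and again at Visits 3 and 4, and only the first measurement precedes all study product. This is a clarification that goes with the change, not a separate error.

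If an unadjusted test is kept, the section should at least name the variable as change in BSIT from Visit 2 pre-dose to Visit 6.

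Cost: two or three sentences and one degree of freedom. No new data, visits or participants.
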